In a preliminary study conducted on 20 cirrhotic subjects, 12 cases of successful puncture for ascites using both Kara-hoc and conventional method were performed, 5 cases of success only with Kara-hoc, and only 1 case of success with conventional method, with a difference of 20%, and a total of 61 cases were required, and 80 cases were required when the drop-out rate of 30% was taken into account.

McNemar Test Analysis

Numeric Results for Two-Sided Test

Power	N	P10	P01	Difference (P10-P01)	Proportion Discordant	Odds Ratio	Alpha	Beta
0.80516	61	0.250	0.050	0.200	0.300	5.000	0.050	0.19484

References

- Schork, M. and Williams, G. 1980. 'Number of Observations Required for the Comparison of Two Correlated Proportions.' Communications in Statistics-Simula. Computa., B9(4), 349-357.

7-5. Research Subject Recruitment Plan

Registered patients are recruited for patients with cirrhosis who require therapeutic ascites puncture due to intractable ascites among patients with cirrhosis who have visited the gastroenterology department outpatient department, ward, and emergency room.

7-6 . Additional protection measures in case of inclusion of vulnerable research subjects

Vulnerable subjects, such as children, pregnant women, and patients with hepatic encephalopathy, who are likely to have difficulty obtaining informed consent due to cognitive decline, were excluded from the study.

8. Expected study period

[figure not shown]
From IRB approval date to December 31, 2022

9. Research method (including observation/inspection items)

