13. Safety Assessment

Measure the pulse rate and blood pressure before and after multiple puncture, and check the properties of the liquid drained immediately after puncture to check for bleeding or intestinal perforation.

14. Data and Statistical Analysis

Comparison of the success rate of ascites puncture using the conventional method and the Karahoc device is a procedure that is repeated once in the same patient, so the influence of other confounding variables can be excluded and analyzed using the McNemar test. Multivariate analysis is performed using logistic regression for factors involved in treatment success in the entire patient group. Patient and operator satisfaction is quantitatively measured using Visual Analogue Scale, and then the average value of satisfaction is compared through t-test.

15. Secruing research ethics

The procedures stipulated in this protocol will ensure that researchers comply with the fundamental spirit of the GCP and the Declaration of Helsinki in conducting, evaluating and recording the results of this study, and will be implemented in accordance with the KGCP, the Law on Bioethics and Safety and related regulations.

This research protocol and its changes, (subject written consent and) related to information provided to the subject, are submitted to the IRB of the conducting institution to obtain formal approval for the conduct of the study in accordance with domestic regulations, and the IRB for conducting the study. The study will not be conducted prior to receipt of the documentation relevant to the decision.

16. Matters concerning the protection of personal information of research subjects

In order to protect the information of the research subjects, unnecessary personal identifiers of the collected data are removed. In particular, in the case record, the patient's name, resident registration number, Chart No. etc. should not be recorded, and the identifier code linked to personal information is managed separately. In addition, when presenting research results, make sure to present them in a form that cannot confirm the identity of the individual.

17. Research subject information and consent form

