The personal information to be collected is gender, date of birth, height, weight, disease name, past medical history, and blood test findings, and sensitive information is not included in the personal information to be collected. The purpose of collecting and using the above items is for the academic purpose of analyzing all patients to find out what factors cause a significant difference during ascites puncture, and it is not used for any other purpose.

Clinical trial schedule

Observation and inspection items	Screening	Intervention	
	Session 0 ¹⁾	Session 1 ¹⁾	Session 2
Subject consent	●		
Basic information	●		
Physical Exam/Vital Signs	●	●	●
Laboratory test ⁷⁾			
Hematology test	●	●	●
Blood coagulation test	●	●	●

Serum biochemical test	●	●	●
Radiologic examination	●		
Inclusion/Exclusion criteria	●		
Randomization ²⁾		●	
Therapeutic ascites puncture		●	●
Confirmation of puncture success		●	●
Confirmation of stability (adverse reaction)		●	●

1) Session 0 and session1 can be identical

2) Randomization is performed if the selection/exclusion criteria are met after confirming the screening test results. If randomization is a kara-hoc set, session 1 uses a kara-hoc set, session 2 uses a vascular catheter, and if randomization is a vascular catheter, session 1 uses a vascular catheter and seesion 2 uses a kara-hoc set.

22. References

1. Iwakiri Y Pathophysiology of portal hypertension. *Clin Liver Dis.* 2014;18:281-291

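### The logistic regression for factors of success has no limit on factors, although the pilot rates imply only about 28 to 31 failed punctures (40 if all 80 patients complete)

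*Combined protocol and SAP*

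**What the plan says.** Section 6 lists factors of successful puncture as secondary purpose d. The whole analysis plan for it is one sentence in Section 14: "Multivariate analysis is performed using logistic regression for factors involved in treatment success in the entire patient group". Section 21 lists seven groups of collected items: gender, date of birth, height, weight, disease name, past history and blood tests. It says they serve "to find out what factors cause a significant difference during ascites puncture". The schedule table adds haematology, coagulation and biochemistry panels, so the number of single variables could be well above seven.

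No section gives a factor list, a maximum number of terms, a selection rule, shrinkage, a multiplicity rule, an exploratory label, or a way to handle two punctures from the same patient. Section 7-4 sizes the trial for the McNemar test only and states no expected number of failures.

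**The concern.** The information in a logistic model is limited by the rarer outcome, which here is failure (less than 3 L drained). With many terms per failure, maximum likelihood pushes coefficients away from zero and sometimes does not converge. The plan describes an open search for significant factors and sets nothing to restrain it.

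Two different faults could follow. One is exaggerated odds ratios, which come from sparse failures. The other is false factors, which come from testing many candidates and from counting each patient twice as if independent. At stake is the credibility of one stated secondary purpose. The comparison of the two devices does not depend on it.

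**Working it through.** **Inputs (Section 7-4).** The pilot had 20 patients: "12 cases of successful puncture for ascites using both Kara-hoc and conventional method were performed, 5 cases of success only with Kara-hoc", then "only 1 case of success with conventional method, with a difference of 20" percent. By subtraction both methods failed in 20 − 12 − 5 − 1 = 2. Failure rates are (1 + 2)/20 = 15% with Kara-hoc and (5 + 2)/20 = 35% with the conventional catheter, or 0.50 expected failures per completing patient.

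**Plan's own figure.** The power row reads "0.80516 61 0.250 0.050" (power, N, P10, P01), two-sided alpha 0.05. Take the exact two-sided McNemar test. Sum over the number of discordant pairs m ~ Binomial(61, 0.30) the probability of rejection when Kara-hoc wins each discordant pair with probability 0.25/0.30. This gives 0.80516 at N = 61 and 0.7973 at N = 60, so the stated figure is reproduced.

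**Completers.** The plan says "a total of 61 cases were required, and 80 cases were required when the drop-out rate of 30% was taken into account". A 30% loss from 80 leaves 80 × 0.70 = 56 pairs. The range to consider is therefore 56, 61 and 80.

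**Failures and failures per variable.** Failures = pairs × 0.50.

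| Pairs | Failures | Per variable, 3 variables | 7 | 10 | 12 |
|---|---|---|---|---|---|
| 56 | 28 | 9.3 | 4.0 | 2.8 | 2.3 |
| 61 | 30.5 | 10.2 | 4.4 | 3.1 | 2.5 |
| 80 | 40 | 13.3 | 5.7 | 4.0 | 3.3 |

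**Imprecision.** The pilot had 10 failures in 40 punctures. Per patient there were 0, 1 or 2 failures in 12, 6 and 2 patients: mean 0.5, variance (12 × 0.25 + 6 × 0.25 + 2 × 2.25)/19 = 0.474, standard error √(0.474/20) = 0.154. A rough 95% interval is 0.5 ± 1.96 × 0.154, or 0.20 to 0.80 failures per patient. At 61 pairs that is about 12 to 49 failures.

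**Bias of ordinary maximum likelihood.** Pairs were simulated from the pilot cells 0.60/0.25/0.05/0.10 with irrelevant covariates. The model included a device term, whose true pooled log odds ratio is ln[(0.85/0.15)/(0.65/0.35)] = 1.116.

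- 61 pairs, one set of runs: ordinary 1.21, 1.23 and 1.31 with 2, 7 and 12 covariates (8%, 10% and 17% high); Firth 1.15, 1.12 and 1.13, with lower root mean squared error and no non-convergence.
- 61 pairs, half the covariates binary at 20%: ordinary 1.28 with 8 and 1.37 with 12 (15% and 23% high), 2-3% non-convergence; Firth 1.14 and 1.17.
- 56 pairs, 12 covariates: 1.41 (26% high), 6% non-convergence.
- 80 pairs: 1.23 with 8 and 1.27 with 12 (10% and 14% high).

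Across 56 to 80 pairs the runs span about 7-15% with 7 or 8 covariates, 14-26% with 12 and 4-8% with two. A genuine patient-level factor (odds ratio 2 per standard deviation) behaves similarly at 56-61 pairs: its log odds ratio is overstated by 6-10% with 3 factors, 15% with 7 and 20-22% with 10.

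**False factors when none is real.** Independent tests at 5% give 1 − 0.95^k: 14%, 30% and 46% for k = 3, 7 and 12. With both punctures per patient kept in an unclustered model, the chance of at least one is about 23-25% with 3, 46% with 7, 47% with 8 and about 65% with 12 (63% in one set of runs). The error per factor is about 8-11% instead of 5%. At 80 pairs the figure with 7 factors is 45%, almost unchanged. With Firth but no clustering it is still about 35%.

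**The case against.** The strongest reply is that the number of covariates is nowhere stated. The item list stands in a confidentiality section and explains why personal data are collected; it is not a model specification. A laboratory panel in a visit schedule is not a panel of regressors. With two or three well-chosen factors the bias is below 10%. Even with 8 covariates it is about 0.16 on the log scale, about a third of the coefficient's standard error of roughly 0.47. This stands, and it makes the inflation conditional. It does not remove the gap: the only stated purpose of the items is a search for factors, and nothing limits it.

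Four stronger readings are tempting, and the documents do not support them.

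- *Few failures will cause chance factors to be reported.* This is a probability, and it hardly moves between 56 and 80 pairs. It comes from multiplicity and ignored pairing.
- *The overfitted model will contradict the primary result.* Section 7-4 gives a paired odds ratio of 5.0 (log 1.61); the pooled value is 1.116 before any bias. The two differ because one is conditional and the other marginal. Overfitting moves the pooled value towards 1.61, not away.
- *The 8 to 9 Kara-hoc failures (56 × 0.15 = 8.4; 61 × 0.15 = 9.15) are the limit.* Section 14 specifies the entire patient group, and no Kara-hoc-only model is planned.
- *The plan chose ordinary maximum likelihood.* That is inferred from the absence of any stated alternative.

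It is also fair to say that the factor analysis is missing from the secondary evaluation items in Section 9, which lowers its weight.

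**Conclusion.** The point holds in conditional form. The plan sets no limit on factors, while its own pilot implies about 28 to 31 failures, or 40 with complete follow-up. If seven or more items are entered, ordinary estimation has about 4 to 6 failures per variable or fewer. It would then overstate log odds ratios by amounts that are moderate with 7 or 8 covariates, larger with 12 and small with two, with occasional non-convergence. The risk of false factors, a little under one half with 7 covariates and about two thirds with 12, is a separate fault with a separate cause.

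This rests on the pilot rates, on an assumed number of covariates, on simulated irrelevant covariates, and on reading the plan's silence as ordinary, unclustered estimation. Severity is modest: one secondary purpose is affected and the primary analysis is not.

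**What to change.** Amend Section 14 as follows.

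1. Use Firth-penalised logistic regression in place of ordinary logistic regression, with standard errors clustered by patient. The penalty addresses bias and non-convergence; the clustering addresses the two punctures per patient.
2. Name a short list of factors before the database is opened, and do no p-value-based selection. The list is what limits multiplicity, which the penalty does not cure. Its exact length is the investigators' choice; the table of failures per variable shows what each length costs.
3. Report all odds ratios with 95% intervals, label the analysis exploratory, and state that the device conclusion rests on the McNemar test.

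The cost is a few sentences and slightly more programming for a penalised, clustered fit. Fewer factors will be examined. No additional patients or data are needed.
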